4.2 Source of the Study Agent

Molecular Imaging Program at Stanford (MIPS)
Satellite Radiochemistry Facility

██
[name]

4.3 Ordering

Ordered in Radiology Information System (RIS), address per above.

4.4 Agent Accountability

RIS is password protected and part of the electronic medical records.

5. IMAGING SPECIFICS

5.1 Modality or Modalities to be used

PET/MRI

5.2 Details of Imaging (ie, dynamic, static, number of scans, etc)

A localizer MRI scan will be performed at 45 minutes after injection of 3 to 7 mCi of ^{68}Ga -PSMA-11 to define the table positions. After correct positioning of the spatial acquisition windows is ensured, the combined PET/MRI acquisition will be initiated with 3 to 5 table positions at a 4-min acquisition time per table position. A volumetric T1 acquisition with fat-water separation and motion correction to enable free-breathing will be obtained at each table position and used for the generation of attenuation maps and for

anatomic allocation of the PET results. Simultaneously with the start of the T1 MRI sequence, the PET acquisition will start at the same table position, thus ensuring optimal temporal and regional correspondence between MRI and PET data. The PET acquisition time will be 4 min per table position, taking delayed acquisition times and radioactive decay into account. As the T1 will take less than 4 minutes, a rapid diffusion weighted MRI will also be performed. After completion of the PET acquisition, the table will be moved to the next table position and the procedure will be repeated. Upon completion of the PET acquisition for all stations, volumetric post-contrast T1- and T2-weighted MR images may be obtained at multiple stations as needed.

The PET emission scan is corrected using segmented attenuation data of the MRI scan. The PET images are reconstructed with a standard iterative algorithm. All images are reformatted into axial, coronal, and sagittal views and viewed with the software provided by the manufacturer (AW, GE Medical Systems).

5.3 Image interpretation

1. ^{68}Ga -PSMA-11 PET

PET images will initially be interpreted in random order at separate reading sessions by 3 board-certified nuclear medicine physicians. Cross-sectional MRI imaging from the PET will be available for anatomic correlate. Final reads for each patient will be interpreted as positive or negative for the presence of pelvic nodal disease, and positive or negative for the presence of osseous metastatic disease and soft tissue metastases outside of the pelvis.

Clinical Follow-up

- a. Prostatectomy: patients without evidence of PSMA-11 PET positive nodal or metastatic disease noted on imaging will undergo radical prostatectomy. If a PSMA-11 PET positive regional pelvic node is noted, the urologist will be informed of the location of the suspicious node and the patient will undergo prostatectomy with nodal dissection.
 - i. Patients with nodes seen on PSMA-11 PET without positive nodes on pathology, will be rescanned with CT or MRI to determine if the suspicious node was thought to be removed. A PSMA-11 PET may be repeated as well at the discretion of the treating physician.
- b. If sites of PSMA-11 PET positive osseous or distant metastatic lesions are noted, the urologist will be informed, and further evaluation including further imaging (bone scan; NaF PET; CT; or MRI cross-section imaging) or targeted biopsy will be performed in order to restage the patient prior to the decision regarding whether or not a prostatectomy will be performed as per the responsible surgeon and standard of clinical care.

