2.5 Study Design

This is a phase 2-3 study with a total of 200 participants with newly-diagnosed intermediate or high-risk prostate cancer scheduled to undergo prostatectomy and lymph node dissection. Eligible participants will undergo baseline assessments at enrollment. Study participants will receive ^{68}Ga -PSMA-11 and undergo a PET/MRI. All patients will first be seen by a Stanford Cancer Institute physician (Drs [name], [name], [name] and [name]) who will refer patients if appropriate on clinical grounds to Dr [name] or his colleagues for this study. The following steps will take place.

1. After signed the informed consent document, participants will be given a copy of the signed form.
2. Participant will be asked to drink 1 to 2 glasses of water before arrival at the clinic
3. Participants will be weighed and vital signs (heart rate and blood pressure) will be recorded
4. Study personnel (eg, technologist) will verify subject identify; radiopharmaceutical identity; dose; and administration route. Participant will be injected IV with 3 to 7 mCi of ^{68}Ga -PSMA-11
5. Participant will void immediately prior to the scan

6. Approximately 50 to 100 minutes after the radiopharmaceutical IV administration, data acquisition will begin in the pelvic region and move toward the head. First, localizer MRI scans will be performed to define the table positions. After correct positioning of the spatial acquisition windows is ensured, the combined PET/MRI acquisition will be initiated with 3 to 5 table positions at a 4-min acquisition time per table position.
7. Vital signs (heart rate and blood pressure) will be recorded again at the completion of the study.
8. Participants will be dismissed.
9. Participants will be contacted at 24 to 72 hours following the scan in order to capture potential late occurring Adverse Events.

The ^{68}Ga -PSMA-11 PET/MRI may be repeated at the completion of treatment to evaluate response to therapy, if requested by the treating physician.

Objectives of the Study

Primary

- Sensitivity, specificity, positive and negative predictive value of ^{68}Ga -PSMA-11 PET/MRI for the detection of regional nodal metastases compared to pathology at radical prostatectomy on a per patient basis using nodal regional correlation.

Secondary

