3. PARTICIPANT SELECTION AND ENROLLMENT PROCEDURES

3.1 Inclusion Criteria

- ≥ 18 years-old
- Biopsy-proven prostate adenocarcinoma
- Planned prostatectomy with lymph node dissection
- Intermediate to high-risk disease (as determined by elevated PSA [$PSA > 10$], T-stage [$T2b$ or greater], Gleason score [Gleason score > 6] or other risk factors)
- Able to provide written consent.
- Karnofsky performance status of ≥ 50 (or ECOG/WHO equivalent)
- Diagnostic CT or MRI performed within 90 days of the research PET

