10.3 Analyses Plans

10.3.1 Analysis Population

All patients that undergo prostatectomy and have histology correlates will be included in the analysis for the primary endpoint.

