c) Analysis plan for Primary Aim 1: For this study to reach success, 2 out of the 3 readers will have to demonstrate a detection sensitivity of 65% or greater for nodal metastases. Additionally, 2 out of the 3 readers will have to demonstrate a detection specificity of 90% or greater for regional nodal metastases based upon region as defined below on a per patient level. The sensitivity, specificity, positive and negative predictive value of PSMA-11 PET for the detection on a per patient basis will be determined using the below criteria:

- i) True positive patient:
 - (1) PSMA-11 PET-positive for regional nodes; pathology at prostatectomy positive for regional nodes. Region will be defined by the granularity used by the urologist at time of prostatectomy. Sensitivity will be calculated at a patient level by region, meaning that one correct region would make a true positive on a patient level. Only one node needs to correspond between imaging and pathology for a patient to be considered a true positive.
 - (2) PSMA-11 PET-positive for regional nodes; pathology negative for regional nodes; imaging after prostatectomy demonstrates node was not removed at surgery; and follow-up biopsy or imaging demonstrates presence of nodal disease.
 - (a) Criteria for positive node on follow-up imaging: imaging within 3 to 12 months; the node decreases by more than 30% (for patients undergoing systemic treatment or focal therapy at this site); or increase by more than 20% in short axis diameter in the absence of treatment (with a minimum of 3 mm in change in size).
- ii) True negative patient:
 - (1) PSMA-11 PET-negative for regional nodes; pathology at prostatectomy negative for regional nodes.
- iii) False positive patient:
 - (1) PSMA-11 PET-positive for regional nodes; pathology at prostatectomy is negative; and imaging after prostatectomy demonstrates that node is no longer present.
 - (2) PSMA-11 PET positive for regional node, but pathology at prostatectomy is positive for node but in a different nodal region than that node seen on PSMA-11 PET.

iv) False negative patient:

- (1) PSMA-11 PET negative for regional nodes, but pathology at prostatectomy is positive.

v) Non-evaluable:

- (1) PSMA-11 PET positive for regional nodes; pathology negative for regional nodes; imaging after prostatectomy demonstrates node was not removed at surgery; and no definitive follow-up is available.

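### Section 5.3 names nodal dissection only for PET-positive patients, against the eligibility criteria, and the primary reference standard depends on the PET result in ways the analysis does not address

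*Combined protocol and SAP*

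**What the plan says.** Two sections plan nodal dissection for everyone. Section 2.5 describes 200 participants with "newly-diagnosed intermediate or high-risk prostate cancer scheduled to undergo prostatectomy and lymph node dissection", and the inclusion criteria in 3.1 list "Planned prostatectomy with lymph node dissection".

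Section 5.3, Clinical Follow-up a, then splits the surgical path by PET result:

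- PET-negative: "patients without evidence of PSMA-11 PET positive nodal or metastatic disease noted on imaging will undergo radical prostatectomy". Dissection is not mentioned.
- PET-positive pelvic node: here dissection is named ("the patient will undergo prostatectomy with nodal dissection"). Before that operation, "the urologist will be informed of the location of the suspicious node".
- PET-positive with negative pathology: the patient is rescanned with CT or MRI to see whether the node was removed. No such step applies to PET-negative, pathology-negative patients.

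For the analysis, 10.3.1 states: "All patients that undergo prostatectomy and have histology correlates will be included in the analysis for the primary endpoint". It does not say that the histology must be nodal. In 10.3.2 c, a false negative is "PSMA-11 PET negative for regional nodes, but pathology at prostatectomy is positive", and a true negative needs PET and pathology both negative for regional nodes. Item i(2) counts a PET-positive, pathology-negative patient as a true positive if the node was left behind and later biopsy or imaging shows disease. Without definitive follow-up, item v(1) makes that patient non-evaluable.

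Success is judged on point estimates: two of three readers must reach at least 65% sensitivity, and two of three at least 90% specificity.

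**The concern.** Sensitivity is estimated without bias only if nodal disease is looked for equally hard whatever PET shows. A PET-negative patient with nodal metastases enters the calculation only if nodes are removed and examined. If dissection follows the PET result, false negatives go unseen and sensitivity rises.

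A literal reading of 5.3 would produce that. Section 10.3.1 offers incomplete protection: a PET-negative patient with prostate histology but no nodes is not clearly excluded, and if such patients are excluded the bias in sensitivity remains.

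Two further steps depend on PET whatever 5.3 intends. The surgeon is directed to a node only when PET is positive, and no section fixes a dissection template or blinds the surgeon or pathologist to PET. The post-operative second look also applies only to PET-positive patients and can only add true positives, never false negatives. With point-estimate success criteria, small shifts can decide the outcome.

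**Working it through.** **Plan figures.** The plan gives no figure for verification by PET result, so there is none to reproduce on this point. Its sample size of 61 node-positive patients (10.2.1) does reproduce, as a one-sided one-sample test of 65% against 45% at alpha 0.01 and 80% power: [(2.326·√(0.45·0.55) + 0.842·√(0.65·0.35))/0.20]² = 60.7, rounded up to 61. That figure does not enter what follows.

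**Inputs.** From 10.2.1: 200 enrolled, 25% without prostatectomy, 30% node-positive, PET sensitivity 65%. Specificity of 90% is assumed, taken from the success criterion in 10.3.2 c.

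- Operated: 200 × 0.75 = 150. Node-positive: 150 × 0.30 = 45. Node-negative: 105.
- TP = 45 × 0.65 = 29.25; FN = 15.75; TN = 105 × 0.90 = 94.5; FP = 10.5.

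**Model.** Let f be the share of node-positive, PET-negative patients whose disease the reference standard finds, relative to PET-positive patients. The documents give no value, so f is an assumption between 0 and 1. For specificity, the same share is assumed to apply to node-negative, PET-negative patients.

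- Apparent sensitivity = 29.25/(29.25 + 15.75f)
- Specificity, unverified PET-negative patients excluded = 94.5f/(94.5f + 10.5)
- Specificity, undetected disease counted as pathology-negative = (94.5 + 15.75(1 − f))/(94.5 + 15.75(1 − f) + 10.5)

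| f | Sensitivity | Specificity, excluded | Specificity, counted negative |
|---|---|---|---|
| 1 | 65.0% | 90.0% | 90.0% |
| 0.8 | 29.25/41.85 = 69.9% | 75.6/86.1 = 87.8% | 97.65/108.15 = 90.3% |
| 0.5 | 29.25/37.125 = 78.8% | 47.25/57.75 = 81.8% | 102.375/112.875 = 90.7% |

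Sensitivity rises equally under both treatments. Specificity falls under one and rises slightly under the other, so the handling rule matters for the 90% criterion.

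**Effect on the 65% line.** A true sensitivity S reads 65% when f = 0.35·S/(0.65·(1 − S)). For S = 55% this is 0.1925/0.2925 = 0.66. For S = 45%, the plan's value for conventional imaging, it is 0.1575/0.3575 = 0.44.

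**Reclassification under i(2).** Each reclassified patient adds one to numerator and denominator. As an illustration, 29/45 = 64.4% misses the criterion, while (29 + 1)/(45 + 1) = 30/46 = 65.2% meets it.

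**Surgeon direction.** Suppose 3 to 5 of the 29 true positives were found only because PET gave the location. Without them sensitivity would be 26/42 = 61.9% or 24/40 = 60.0%, so direction adds 2.5 to 4.4 points. This is an upper bound for those assumed counts, because a node left behind could still give a true positive under i(2).

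**Exclusion versus correction at f = 0.5.** Among verified PET-negative patients, 7.875/(7.875 + 47.25) = 14.3% are node-positive. Applied to all 110.25 PET-negative patients, that gives 15.75 false negatives and restores 65%. Exclusion alone leaves 78.8%. The correction assumes that verified PET-negative patients represent the rest.

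**The case against.** The strongest reply is that 5.3 never says PET-negative patients skip dissection. Elsewhere the protocol uses prostatectomy, or radical prostatectomy, for the operation that yields nodal pathology: the primary objective compares nodal findings with pathology at radical prostatectomy, 10.1 takes nodal histology from prostatectomy, and 10.3.2 b examines prostatectomy specimens for nodal metastasis. The definitions in 10.3.2 and the assumed 65% sensitivity also presuppose false negatives. This stands: shorthand is a plausible reading, and under it missing histology may not arise.

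A reader might infer that PET-negative patients will not be dissected, so that sensitivity would be 100% by construction with about 110 patients (15.75 + 94.5) lacking a reference result. The documents do not support that; it needs f = 0, and they give no dissection fraction. Nor do they support the inference that PET would beat conventional imaging whatever its accuracy. The apparent sensitivity of conventional imaging would change too, depending on its agreement with PET, which is not given.

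It can also be said that 10.3.2 already requires negative pathology for a true negative and already records node location and number. That is right, and it makes the remedy smaller. It does not remove the two PET-dependent steps, and excluding unverified patients does not cure partial verification.

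**Conclusion.** The concern holds as a conflict by omission between 5.3 and sections 2.5, 3.1 and 10.3.2, together with a reference standard that depends on PET under either reading. Unequal verification biases sensitivity upward. The effect on specificity depends on how PET-negative patients without nodal histology are handled.

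The size cannot be obtained from the documents. With a true sensitivity of 65%, the apparent value is 65% at f = 1, 69.9% at f = 0.8 and 78.8% at f = 0.5. At f = 0.5 an assumed specificity of 90% reads 81.8% if unverified patients are excluded. If everyone is dissected as planned, f may be near 1 and what remains is the effect of surgeon direction and of i(2), also of unknown size.

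**What to change.** 1. Reconcile sections 2.5, 3.1 and 5.3 on who has nodal dissection. Which surgical rule applies is not judged here, and nothing in this point changes what the surgeon is told.
2. In 10.3.1, require nodal histology specifically, so that a PET-negative patient without it is never counted as a true negative.
3. Report by PET result the number of patients with nodal histology and the node counts already recorded under 10.3.2 b.
4. Add a sensitivity analysis with surgical nodal histology as the only reference, without reclassification under i(2). State in advance how the affected patients are counted: sensitivity is the same whether they are false positives or set aside, but specificity is not.
5. If some PET-negative patients lack nodal histology, add an analysis correcting for partial verification over a stated range of assumptions.

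An analysis excluding nodes removed because of the PET location is not advised. Those that prove positive are histologically confirmed metastases, and excluding them could recode a node-positive patient as pathology-negative.

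The cost is a wording change, one table and one or two extra analyses. The downside is a sensitivity estimate that may be less favourable.

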6. STUDY PROCEDURES

6.1 Criteria for Removal from Study

The Protocol Director may withdraw subjects from the study for one or more of the following reasons: failure to follow the instructions of the Protocol Director and/or study staff; determination that continuing the participation could be harmful to the subject; the study is cancelled or other administrative reasons.

6.2 Alternatives

The alternative is to not participate in the study.

7. STUDY CALENDAR

	Pre-Study	Scan Date	24 to 72 Hours Post-Study	12 Months
Informed consent	X			
Demographics	X			
Medical history	X			
⁶⁸ Ga-PSMA-11		X		
Follow-up Call to Participant			X	
Data analysis				X

8. ADVERSE EVENTS AND REPORTING PROCEDURES

8.1 Potential Adverse Events

The administration of the radioactive substance will feel like a slight pinprick when given by IV injection. Patients who are claustrophobic may feel some anxiety while positioned in the scanner. Also, some patients find it uncomfortable to hold one position for more than a few minutes. The subjects will not feel anything related to the radioactivity of the substance in their body. Because the radioactivity is very short-lived, the radiation exposure is low. The substance amount is so small that it does not affect the normal processes of the body.

This research study involves exposure to radiation from one ⁶⁸Ga-PSMA-11 PET/MRI. The effective dose from one typical maximum of 259 MBq (range: 3 to 7 mCi) administration of ⁶⁸Ga-PSMA-11 is 6.68 mSv. There is no radiation exposure from MRI. Therefore, the effective dose from one ⁶⁸Ga-PSMA-11 PET/MRI is 6.68 mSv, approximately equal to 13% of the limit that radiation workers (eg, a hospital X-ray technician) are allowed to receive in one year.

8.2 Adverse Event Reporting

We do not anticipate hazardous situations for the subjects as a result of this protocol. However, standard of care procedures will be in place for verification of correct radiopharmaceutical dose and route of administration. The study Principal Investigator (PI) or his designee will report all serious adverse events (per 21CFR§312.32) to the Stanford CCTO Safety Coordinator within 10 working days of becoming aware of the event (5 days if the event is life-threatening or resulted in death) using the Adverse Events Communication Form. If the principal investigator determines the unanticipated adverse effect presents an unreasonable risk to subjects, the study will be terminated as soon as possible, but no later than 5 working days after the PI makes the determination and no later than 15 working days after first receiving notification of the effect.

9. REGULATORY CONSIDERATIONS

9.1 Institutional Review of Protocol

The protocol, the proposed informed consent and all forms of participant information related to the study (eg, advertisements used to recruit participants) will be reviewed and approved by the Stanford IRB. Any changes made to the protocol will be submitted as a modification and will be approved by the IRB prior to implementation. The Protocol Director will disseminate the protocol amendment information to all participating investigators.

9.2 Data Management Plan

The CRFs will be stored in a locked office in the Nuclear Medicine clinic. Records will be kept using OnCore.

During the clinical investigation, the Protocol Director will evaluate the progress of the trial, including periodic assessments of data quality and timeliness, participant recruitment, accrual and retention, participant risk versus benefit, performance of trial sites, and other factors that can affect study outcome. Monitoring of the trial will occur every 8 weeks and a record of monitoring activities will be maintained by the study team.

The Stanford Cancer Institute Data and Safety Monitoring Committee (DSMC) will audit study related activities to determine whether the study has been conducted in accordance with the protocol, local standard operating procedures, FDA regulations, and Good Clinical Practice (GCP). This may include review of regulatory binders, case report forms, eligibility checklists, and source documents. In addition, the DSMC will regularly review serious adverse events and protocol deviations associated with the research to ensure the protection of human subjects. Results of DSMC audits will be communicated to the IRB and the appropriate regulatory authorities at the time of continuing review, or in an expedited fashion, as needed.

10. Statistical Considerations and Evaluation of Results

10.1 Study Endpoints

Primary endpoints:

- PSMA-11 PET results for regional nodal disease.
- Nodal histology results from prostatectomy.

These will be expressed as range (mean \pm SD) of number of lymph nodes identified by PET and by dissection during surgery plus histopathology.

10.2 Determination of Sample Size and Accrual Rate

10.2.1 Sample Size and Power Estimate

The estimated sample size will be 200 patients to adequately power the primary aim. The power analysis will be based on the comparison of sensitivity between conventional imaging and PSMA-11 PET. With a power of 80% and a significance level of 0.01, a sample size of 61 patients with nodal metastases is required. The following assumptions are made:

- i. 30% of intermediate to high-risk patients have nodal metastases at prostatectomy.

- ii. 25% of patients will not undergo the planned prostatectomy. Patients that do not undergo prostatectomy will not be included in the analysis population, and will not undergo central imaging review.
- iii. Conventional imaging has a 45% detection sensitivity for nodal metastases on a per-patient basis (2).
- iv. PSMA-11 PET has a 65% detection sensitivity for nodal metastases on a per-patient basis.

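### By Section 10.2.1's own assumptions, 200 enrolled patients yield about 45 node-positive patients, not the 61 said to be needed for 80% power

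*Combined protocol and SAP*

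**What the plan says.** Section 10.2.1 opens with "The estimated sample size will be 200 patients to adequately power the primary aim". It then says what the calculation rests on: "The power analysis will be based on the comparison of sensitivity between conventional imaging and PSMA-11 PET". The requirement is "With a power of 80% and a significance level of 0.01, a sample size of 61 patients with nodal metastases is required".

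The assumptions are listed beneath it:

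- Prevalence: "30% of intermediate to high-risk patients have nodal metastases at prostatectomy".
- Loss: "25% of patients will not undergo the planned prostatectomy", and "Patients that do not undergo prostatectomy will not be included in the analysis population".
- Comparator: "Conventional imaging has a 45% detection sensitivity for nodal metastases on a per-patient basis".
- Investigational scan: "PSMA-11 PET has a 65% detection sensitivity for nodal metastases on a per-patient basis".

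Sections 2.5, 10.2.2 and 10.4 (40 a year for 5 years) all treat 200 as the number enrolled. Section 10.3.1 restricts the primary analysis to operated patients with histology.

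**The concern.** The requirement is expressed in node-positive patients, while the design is expressed in enrolled patients. Two stated rates link them: the share operated on and the share node-positive at operation. Applying the prevalence alone to 200 gives 60, close to 61. Applying the loss as well gives a much smaller number. The 25% loss appears to have been listed but not used.

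Section 10.2.1 is the only justification given for 200, and it claims 80% power. The comparison behind that figure, PET against conventional imaging for sensitivity, is exploratory in Section 2.5 and tested by a paired McNemar test in Section 10.3.4. If that test is not significant, a reader would weigh the result against a power the design does not have.

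**Working it through.** **Inputs.** All are from Section 10.2.1: 200 enrolled; 25% not operated on and excluded; 30% node-positive at prostatectomy; sensitivity 45% (conventional) and 65% (PET); significance level 0.01; power 80%; 61 node-positive patients required. The test, its sidedness and the PET versus conventional discordance are not stated. Wherever they are used below they are assumptions.

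**1. Reproducing 61.** A one-sample test of 65% against a fixed 45%, one-sided 0.01, normal approximation:

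n = [(z₀.₉₉√(0.45 × 0.55) + z₀.₈₀√(0.65 × 0.35)) / 0.20]² = [(2.326 × 0.4975 + 0.842 × 0.4770) / 0.20]² = 60.7, rounded up to 61.

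The two-sided version gives 70.8. A paired McNemar calculation, n = [(z_α√ψ + z₀.₈₀√(ψ − 0.04)) / 0.20]² with ψ the total discordance, also gives about 61 at ψ = 0.25 to 0.255 one-sided (60.0 to 61.2) or ψ = 0.22 two-sided (61.2). So 61 is attainable from the stated sensitivities. The fault lies in the step from 61 to 200.

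**2. Expected node-positive patients.**

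- Operated: 200 × 0.75 = 150.
- Node-positive: 150 × 0.30 = 45. The shortfall is 61 − 45 = 16, or 16/61 = 26%.
- Without the loss: 200 × 0.30 = 60, and 61/0.30 = 203.
- With the loss: 61/(0.75 × 0.30) = 271.1, so 272 enrolled for an expected 61.
- Prevalence needed for 61 among 150: 61/150 = 40.7%, against the stated 30%.

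**3. Could chance close the gap?** With independent patients, the count is Binomial(200, 0.225): mean 45, SD 5.9, 95% range 34 to 57, P(61 or more) = 0.0054.

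**4. Power at 45.** For the one-sample formula: Φ[(0.20√45 − 2.326 × 0.4975) / 0.4770] = Φ(0.386) = 65%. At 61 it returns 80%.

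Readings that reproduce about 61:

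| Test (level 0.01) | Normal approx., n = 45 | Exact, n = 61 | Exact, n = 45 |
|---|---|---|---|
| One-sample, one-sided | 65% | 72% | 60% |
| McNemar one-sided, ψ = 0.25 | 65% | 79% | 57% |
| McNemar one-sided, ψ = 0.255 | 64% | 77% | 56% |
| McNemar two-sided, ψ = 0.22 | 62% | 83% | 59% |

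McNemar power at 45 over other assumed values of ψ, normal approximation with exact in brackets:

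| ψ | One-sided | Two-sided |
|---|---|---|
| 0.20 (the minimum possible) | 77% (82%) | 68% (70%) |
| 0.30 | 55% (45%) | 45% (36%) |
| 0.515 (conditional independence: 0.65 × 0.55 + 0.35 × 0.45) | 32% (26%) | 23% (18%) |

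**5. Precision of the primary estimate.** The Wilson 95% interval at an observed sensitivity of 65% is about 50% to 77% with 45 patients and 52% to 76% with 61.

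**The case against.** The strongest objection concerns importance. The primary success rule in Section 10.3.2 c compares point estimates with thresholds (65% sensitivity and 90% specificity, each for two of three readers) and uses no p-value. The under-powered comparison is exploratory, the loss of precision is small, and the remedy changes only wording. All of that is correct and limits the consequences. It does not make the power statement true, and that statement is the only reason given for 200.

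A second objection is that the replacement power rests on a reconstructed test. The one-sample form appears nowhere in the plan; it is used because it returns 61, and its exact version gives only 72% at 61 and 60% at 45. This stands as a caution: 65% should not be presented as the sponsor's own figure or as the only one.

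Third, one setting does exceed 80% at 45: exact one-sided McNemar at discordance 0.20 gives 82%. There, PET misses no patient whom conventional imaging detects. That setting calls for about 47 patients by normal approximation, and the exact test passes 80% by 45, so it cannot be the calculation that produced 61.

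Finally, omission of the 25% loss is an inference. It gives 203 rather than exactly 200, and the plan does not show the derivation. One other reading would rescue 200: that essentially all patients who miss surgery are node-negative. The plan does not say so, and Section 5.3 makes PET-positive distant disease a reason to reconsider surgery. The rules in Section 10.3.2 c for unremoved and non-evaluable nodes could shift the count slightly, but they are unquantified and play no part in 10.2.1.

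**Conclusion.** The concern holds. The mismatch between 45 and 61 needs only the rates stated in Section 10.2.1 and the analysis population in Section 10.3.1; it does not depend on the choice of test. The 0.5% chance of reaching 61 additionally assumes independent patients.

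The claim of 80% power is therefore unsupported as written. How far power falls depends on a test and a discordance that the plan does not give. Every reading found that yields about 61 puts power at 45 well below 80%, and greater discordance lowers it further. The consequence falls on how the exploratory comparison is interpreted, not on the primary success rule.

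**What to change.** Keep 200 and correct Section 10.2.1:

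- State that 200 enrolled is expected to give about 150 operated and about 45 node-positive patients, before the small, unquantified reclassifications in Section 10.3.2 c.
- Replace the 80% with the power at 45, naming the test and its sidedness. If the one-sample, one-sided 0.01 formula is what was used, its normal-approximation value is about 65% (exact 60%). Show beside it the paired McNemar power over a labelled range of assumed discordance, for example 0.20 to 0.515, because McNemar is the test planned in Section 10.3.4.
- Add the expected Wilson interval for sensitivity with 45 patients.

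The cost is protocol wording and a less favourable stated power. Patients, procedures and accrual are unchanged.

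Enlarging the trial is not preferred. Enrolling 272 makes 61 the expected count but gives only a 54% chance of reaching it; an 80% chance needs about 296. At 40 a year, these take 272/40 = 6.8 and 296/40 = 7.4 years. Section 3.4 already sets study completion at 48 months, which is shorter than the five years of accrual in Section 10.4.
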